9.4.4 Six Minute Walk Test

A six minute walk test will also be administered at the Baseline and 12 month visits. The distance walked (in meters) will be assessed, as will the number of laps completed and whether the subject stopped or paused before 6 minutes. The level of shortness of breath and level of fatigue will be assessed both pre- and post-test on a 0-10 scale.

All collected information will be listed by subject and time point. The distance walked at each visit, and change from baseline in distance walked, will be summarized by time point and treatment arm. The change from baseline in distance walked at 12 months will be analyzed using an ANCOVA model with the distance walked as the dependent variable, and treatment arm and baseline distance walked as covariates.

9.4.5 Freedom from Atrial Fibrillation

Freedom from atrial fibrillation will be analyzed as described for the primary efficacy endpoint, using the ITT, mITT, and PP populations. Freedom from AF is defined in Section 7.4.4. Imputation of AF freedom, as described in Section 7.2, will be utilized.

9.4.6 Freedom from Atrial Fibrillation, regardless of AADs

Freedom from atrial fibrillation, regardless of AADs, will be analyzed as described for the primary efficacy endpoint. Freedom from AF is defined in Section 7.4.4; this analysis will not consider the use of new or increased doses of Class I/III AADs to be treatment failure. Imputation of AF freedom, as described in Section 7.2, will be utilized where appropriate.

9.5 Exploratory Efficacy Analysis

9.5.1 Reduction from Baseline AF Burden at 18 Months

The reduction in AF burden from baseline to 18 months will be categorized and analyzed as described for the reduction in AF burden at 12 months (Section 9.4.1).

This analysis will be performed on the ITT population. No imputation will be performed for missing data.

9.5.2 Change in Left Ventricular Ejection Fraction (LVEF)

The left ventricular ejection fraction, defined as a percentage, will be evaluated via echocardiography at the Baseline and 6 month visits. The change from baseline in LVEF will be analyzed using an ANCOVA model with the LVEF as the dependent variable, and treatment arm and baseline LVEF as covariates.

9.5.3 Change in Left Atrial Size

The size of the left atrium, in centimeters, will be evaluated via echocardiography at the Baseline and 6 month visits. The change from baseline in left atrial size will be analyzed using an ANCOVA model with the left atrial size as the dependent variable, and treatment arm and baseline left atrial size as covariates.

9.5.4 Hospitalizations

Hospitalizations will be recorded including start date, duration, and reason for hospitalization (cardiovascular, AF, other). All information will be listed by subject and date. The number of hospitalizations and total number of days hospitalized will be summarized by treatment arm as follows:

- Hospitalizations in the 12 months prior to study procedure (defined hospitalizations with start dates on or after the 365th day before the study procedure, and before the study procedure date).
- Hospitalizations for the 12 month period beginning on the day after the 6 month visit (see Section 7.4.2) through the 365th day after the 6 month visit.

The change in the number of hospitalizations between the two periods will be calculated for each subject as the number of hospitalizations in the 6-18 month period minus the number of hospitalizations in the 12 months prior to the study procedure. The change in the total number of days hospitalized will be calculated similarly. The change will not be calculated for subjects who withdraw from the study within 18 months after study procedure, and they will be excluded from analyses. No imputation will be performed.

The difference between treatment arms in the change in the number of hospitalizations will be analyzed using a Poisson model with treatment arm and the number of hospitalizations in the 12 months prior to the study procedure as covariates. The difference between treatment arms in the change in the total number of days hospitalized will be analyzed similarly. Both analyses will be performed on the ITT population.

9.5.5 **Rhythm Disturbance Treatments**

Rhythm disturbance treatments are defined as cardioversion (either electrical or pharmacological), AAD therapy, endocardial catheter ablation, or convergent procedure. The dates of treatments, as recorded on the Rhythm Disturbance Evaluation eCRF, will be used to determine the type and date of occurrence. The number of rhythm disturbance treatments will be summarized by treatment arm as follows:

- Rhythm disturbance treatments in the 12 months prior to study procedure (defined hospitalizations with start dates on or after the 365th day before the study procedure, and before the study procedure date).
- Rhythm disturbance treatments for the 12 month period beginning on the day after the 6 month visit (see Section 7.4.2) through the 365th day after the 6 month visit.

The change in the number of rhythm disturbance treatments between the two periods will be calculated for each subject as the number of rhythm disturbance treatments in the 6-18 month period minus the number of rhythm disturbance treatments in the 12 months prior to the study procedure. The change will not be calculated for subjects who withdraw from the study within 18 months after study procedure, and they will be excluded from analyses. No imputation will be performed.

The difference between treatment arms in the change in the number of rhythm disturbance treatments will be analyzed using a Poisson model with treatment arm and the number of rhythm disturbance treatments in the 12 months prior to the study procedure as covariates. This analysis will be performed on the ITT population.

9.5.6 **≥75% Reduction in AF Burden**

The percent change from baseline at 12 months will also be categorized as ≥75% reduction (percent change ≤ -75%) or <75% reduction (percent change >-90%). The proportion of subjects achieving ≥75% reduction at 12 months will be compared between treatment arms using Fisher's Exact test, as described in Section 9.4.1.

This analysis will be repeated for the subsets of subjects described for the analysis of 90% reduction of AF burden. No imputation will be performed for missing data.

9.5.7 **≤12% Overall AF Burden**

Subjects will be categorized as having no more than 12% AF burden or >12% AF burden at 6, 12, and 18 months. The proportion of subjects with >12% AF burden will be compared between treatment arms using Fisher's Exact test, as described in Section 9.4.1.

This analysis will be repeated for the subsets of subjects described for the analysis of

90% reduction of AF burden. No imputation will be performed for missing data.

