## 6.7 Continued Long-term Follow-up

### 6.7.1 Month 18 Visit (550 +/- 30 days post index procedure)

Subjects in both study arms will return for a continued long-term post-procedure follow up visit at 18 months to evaluate their progress. The 18 month post procedure assessment will include:

- ECG – subject rhythm evaluation
- 7 Day Holter monitor
- Evaluation of any adverse events
- Evaluation of any major adverse events (MAE)
- Medications – class I and III AADs, other cardiac medications and anticoagulants
- Any AF treatment that was needed
- Hospitalizations and rhythm disturbance treatments following the 6 months post procedure follow-up to the 18 months post-procedure follow-up.

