9.2 Multiplicity Adjustment

The fixed-sequence procedure[1,2] will be used to evaluate the following secondary endpoints. Each of these tests will be tested at the same significance level ($\alpha=0.05$) in this predetermined order. Each endpoint is only tested if the prior endpoint is successful ($p \leq 0.05$). This procedure does not inflate the Type I error rate since the sequence is prospectively specified and no further testing is performed once an endpoint in the sequence fails to show significance ($p > 0.05$)[2]. All tests will be performed on the ITT population. If sufficient data have not been collected during this study to permit the evaluation of a given endpoint, that endpoint should be skipped and the subsequent endpoint evaluated:

- 1) Achievement of $\geq 90\%$ reduction in baseline AF burden at 12 months post-procedure, where subjects with new or increased dosage of Class I/III AADs during the efficacy evaluation period are categorized as not achieving $\geq 90\%$ reduction, using the Fisher's Exact test as described in Section 9.4.1.

- 2) AF freedom during efficacy evaluation period, using the chi-square or Fisher's Exact test as described in Sections 9.4.5 and 9.1, where subjects with new or increased dosage of Class I/III AADs during the efficacy evaluation period are categorized as not achieving AF freedom.
- 3) Achievement of $\geq 90\%$ reduction in baseline AF burden at 12 months post-procedure, regardless of Class I/III AAD usage, using the Fisher's Exact test as described in Section 9.4.1.
- 4) AF freedom during efficacy evaluation period, using the chi-square or Fisher's Exact test as described in Sections 9.4.5 and 9.1, regardless of Class I/III AAD usage.
- 5) Change in AFSS composite score at 12 months post-procedure, using an ANCOVA model as described in Section 9.4.3.
- 6) Change in SF-36 physical health composite score at 12 months post-procedure, using an ANCOVA model as described in Section 9.4.2.
- 7) Change in SF-36 mental health composite score at 12 months post-procedure, using an ANCOVA model as described in Section 9.4.2.
- 8) Change in distance walked during six-minute walk test at 12 months post-procedure, using an ANCOVA model as described in Section 9.4.4.
- 9) Change in left ventricular ejection fraction (LVEF) at 6 months post-procedure, as described in Section 9.5.2.
- 10) Atrial remodeling assessed by a decrease in left atrial size at 6 months post-procedure, as described in Section 9.5.3.

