- 11) Freedom from AF/AFL/AT requiring intervention (emergency visits, cardioversion, urgent care visit, re-ablation, etc.), data permitting.
- 12) Achievement of $\geq 75\%$ reduction in baseline AF burden at 12 months post-procedure, where subjects with new or increased dosage of Class I/III AADs during the efficacy evaluation period are categorized as not achieving $\geq 75\%$ reduction, using the Fisher's Exact test as described in Section 9.4.1.
- 13) Achievement of no more than 12% AF burden at 12 months post-procedure, where subjects with new or increased dosage of Class I/III AADs during the efficacy evaluation period are categorized as not achieving $\leq 12\%$ AF burden, using the Fisher's Exact test as described in Section 9.4.1.
- 14) Freedom from stroke-relevant AF/ AFL/AT-duration (cutoff of 1 hour), data permitting.
- 15) Regression of AF: conversion of persistent to paroxysmal AF, data permitting.
- 16) Prevention in AF progression: time to first episode of persistent AF, data permitting.

Multiplicity tests #1-16 are based on the 12 month data analyses, and will be performed at that time. The following multiplicity tests are based on data collected at the 18 month visit. Therefore, they will be performed after data collection and cleaning is completed for the 18 month visit. As described above, these endpoints will only be evaluated using the fixed-sequence procedure if all of the prior endpoints are significant.

- 17) Success or failure to achieve a 90% reduction from baseline AF burden with and without Class I/III AADs at 18 months post-procedure, where subjects with new or increased dosage of Class I/III AADs during the efficacy evaluation period are categorized as not achieving $\geq 90\%$ reduction, as described in Section 9.5.1.
- 18) Change in number of hospitalizations for the 12 months post-procedure period (6 months to 18 months post- procedure) compared to the number of hospitalizations in the 12 months prior to the procedure, as described in Section 9.5.4, date permitting.
- 19) Change in rhythm disturbance treatments (e.g. electrical or pharmacological cardioversion, AAD therapy, supraventricular ablative therapy) 12 months post-procedure period (6 to 18 months post-procedure) compared to 12 months prior to the procedure, as described in Section 9.5.5, data permitting.

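### Tests 18 and 19 are labelled ITT, but SAP 9.5.4 and 9.5.5 exclude everyone who withdraws within 18 months, and the counting window does not match the 18-month visit

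*SAP*

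**What the plan says.** SAP 9.2 lists "Change in number of hospitalizations for the 12 months post-procedure period" (months 6 to 18 against the year before the procedure) as test 18, and the matching change in rhythm disturbance treatments as test 19. For the whole sequence it states: "All tests will be performed on the ITT population". SAP 5.1 defines ITT as everyone who receives a randomized procedure and does not require completion of follow-up.

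The analysis sections repeat the label. SAP 9.5.4 says "Both analyses will be performed on the ITT population" and SAP 9.5.5 says "This analysis will be performed on the ITT population". Yet both sections state that the change is not computed for "subjects who withdraw from the study within 18 months after study procedure, and they will be excluded from analyses", and that nothing is imputed. The model in each is a Poisson regression on arm and the prior-year count, with no term for time observed.

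The post-procedure window opens the day after the 6-month visit and runs "through the 365th day after the 6 month visit". Protocol 6.7.1 schedules the matching collection at the 18-month visit: "Hospitalizations and rhythm disturbance treatments following the 6 months post procedure follow-up to the 18 months post-procedure follow-up".

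**The concern.** A reader of the results would take an ITT label to mean that all treated subjects are compared. Under the written rule the comparison covers only those who stay to 18 months, and events and follow-up time between month 6 and withdrawal play no part in it. If those who leave differ in event rate from those who stay, and this does not cancel between arms, the estimated arm effect moves in a direction that cannot be known in advance.

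The window raises a second problem that needs no assumption about withdrawal. It is anchored to each subject's own 6-month visit, while collection stops at a separately timed 18-month visit. Days in the window after the last collection count as event-free, and a subject may finish the window and still fall under the exclusion.

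Nothing else in the SAP covers this. The tipping-point and multiple-imputation analyses (SAP 9.3.2 and 9.3.4) apply to the primary endpoint only. For that endpoint SAP 7.2 keeps subjects with missing results and counts them as failures.

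**Working it through.** **Number excluded.** The only sample size in the plan is the primary one (Protocol 9.2, SAP 4): 40% against 65%, two-sided 0.05, 80% power, 2:1. The pooled-variance formula without continuity correction gives 46 control and 92 treatment, 138 in total. Then 46 × 1.10 = 50.6, rounded to 51, and 51 + 102 = 153, which matches the plan. (Dividing instead, 138 / 0.90 = 153.3, so 154.) The plan does not tie its 10% drop-out to month 18. Assuming that it applies there, 153 × 0.10 = 15.3 subjects are excluded, leaving about 92:46. At an assumed 5% to 25% the rule excludes about 8 to 38.

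**Can a bias size be derived?** The documents give no event rates and no reasons for withdrawal, so both illustrations below rest on assumptions.

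*(a) True rate ratio 1; withdrawers have k times the completers' rate in both arms.* With withdrawal fractions dT and dC, the completers' ratio is `(1 − dC + k·dC) / (1 − dT + k·dT)`.
- 10% and 10%: 1.00 for any k.
- dT 5%, dC 10%: 1.05/1.025 = 1.02 (k = 1.5) to 1.20/1.10 = 1.09 (k = 3).
- dT 5%, dC 20%: 1.10/1.025 = 1.07 to 1.40/1.10 = 1.27.
- k = 1: no bias.

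*(b) Planned 65%/40% success; assumed 0.2 hospitalizations per year if AF-free and 0.8 if failed.* The all-subject means are 0.65 × 0.2 + 0.35 × 0.8 = 0.41 and 0.40 × 0.2 + 0.60 × 0.8 = 0.56, a ratio of 0.73. The last column is the completers' log ratio divided by the all-subject log ratio, minus 1.

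| Withdrawal, share of arm (treatment / control) | Who withdraws | Completers' means | Ratio | Change in log effect |
|---|---|---|---|---|
| 10% / 10% | failures only | 0.33/0.90 = 0.367; 0.48/0.90 = 0.533 | 0.69 | +20% |
| 5% / 20% | failures only | 0.37/0.95 = 0.389; 0.40/0.80 = 0.500 | 0.78 | −20% |
| 12.5% / 5% | failures only | 0.31/0.875 = 0.354; 0.52/0.95 = 0.547 | 0.65 | +40% |
| 5% / 20% | failures twice as likely to leave | 0.384/0.95 = 0.405; 0.43/0.80 = 0.538 | 0.75 | −9% |

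Sign and size depend on the assumptions. Equal withdrawal is harmless in (a) but not in (b), where the share of failures differs between arms. What is needed is outcome-related withdrawal whose effect does not cancel between arms. Neither its presence nor its size can be read from the documents.

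**Window against visit.** SAP 3.2 allows the 6-month visit on day 180 ± 30 (150 to 210) and the 18-month visit on day 550 ± 30 (520 to 580).
- Window end: 150 + 365 = 515 to 210 + 365 = 575.
- Largest overrun: 575 − 520 = 55 days.
- The reverse case: a 6-month visit on day 150 closes the window on day 515. A subject who withdraws on day 530 has the whole window observed but has not reached the day-550 target, and is excluded.
- If visit days are uniform and independent (an assumption), an overrun needs the 6-month offset to exceed the 18-month offset by more than 5 days. The probability is (55² / 2) / 60² = 0.42. The mean overrun is 55 / 3 = 18.3 days when there is one, and 0.42 × 18.3 = 7.7 days overall, or 7.7 / 365 = 2.1% of the window.

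**The case against.** The strongest reply is that the exclusion is neutral as to cause and its practical reach is small. Much of that stands.

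- A reader might infer that subjects are dropped for outcome-related reasons. The documents do not support this. The rule covers every withdrawal, and Protocol 6.1 keeps efficacy failures, including those re-ablated, in follow-up. Protocol 12.6 also asks that discontinued subjects who are not lost to follow-up be contacted, where possible, for safety assessments by phone. Outcome-related withdrawal remains a credible risk: the trial is open-label, SAP 10.2 plans a table of adverse events leading to discontinuation, and Protocol 8.2 makes hospitalization a criterion of seriousness.
- A reader might infer that all data collection ends at month 18. That is too strong. The year-2 call (Protocol 6.7.2) still asks about AF treatments and adverse events, so the overrun point is confined to the dedicated hospitalization item. With visit timing alike in both arms, the overrun would not by itself favour either.
- The excluded subjects' hospitalizations are not erased; SAP 9.5.4 lists them by subject and date. They are left out of the change score and its test.
- The endpoints are exploratory health-economics measures that may be evaluated (Protocol 1.4.3, SAP 2.1.4). They come last of 19 tests, depend on the data permitting, and are reached formally only if the earlier tests succeed. The premarket submission follows the 12-month visit (Protocol 1.3).

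None of this removes the mismatch between the ITT label and the exclusion, or supplies a sensitivity analysis for it.

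**Conclusion.** The point holds as a minor one. Followed as written, SAP 9.5.4 and 9.5.5 produce completers-only results under an ITT label. They discard partial follow-up and may be biased if withdrawal is related to outcome. The documents support no specific bias size: the ratios above rest on assumed event rates and assumed withdrawal patterns, and they move in both directions. The figure of about 15 subjects excluded assumes that the planned 10% drop-out applies at month 18.

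The mismatch between window and visit follows directly from the plan's own visit windows. Hospitalization counts can include up to 55 unobserved days, and a completed window does not guarantee inclusion. The 42% and 7.7-day figures rest on uniform visit timing. The primary conclusion and the 12-month tests are unaffected.

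**What to change.** Replace the exclusion in SAP 9.5.4 and 9.5.5:

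- Include every ITT subject who enters the window. Model the post-period count with arm and the prior-period count as covariates.
- Censor at the earliest of day 365 of the window, the last data collection for that item, withdrawal or death, and add log(days observed) as an offset.
- State that the endpoint thereby becomes a post-period rate adjusted for the prior count, no longer a change between two fixed 12-month periods.
- Report by arm how many left before and during the window.
- Keep the completers analysis, labelled as such, as a sensitivity analysis.

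The sponsor should first confirm what is held for withdrawers. AF treatments are documented at month 12 (Protocol Table 1), so partial data should exist for test 19. The dedicated post-procedure hospitalization item is scheduled only at month 18. If partial hospitalization data are not held, the minimum change is to relabel the analysis as completers and report exclusions by arm.

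The cost is SAP wording and a respecified count model that uses recorded dates. The downside is that the offset assumes a constant event rate within the window, and subjects who leave before month 6 still contribute nothing.

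### SAP 9.5.4 and 9.5.5 apply a Poisson model to a change that can be negative, so tests 18 and 19 cannot be run as written; if the post-period count is meant, overdispersion is not dealt with

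*SAP*

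**What the plan says.** SAP 9.5.4 forms a change for each subject: the number of hospitalizations in the 6-18 month period "minus the number of hospitalizations in the 12 months prior to the study procedure". It then states that the arm difference in "the change in the number of hospitalizations will be analyzed using a Poisson model with treatment arm" and the prior-year number as covariates. For length of stay it adds: "The difference between treatment arms in the change in the total number of days hospitalized will be analyzed similarly".

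SAP 9.5.5 follows the same pattern. The change is the 6-18 month number "minus the number of rhythm disturbance treatments in the 12 months prior to the study procedure", and the arm difference in "the change in the number of rhythm disturbance treatments will be analyzed using a Poisson model with treatment arm" and the prior number as covariates.

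Neither section names a dependent variable other than the change, and neither mentions a dispersion parameter, a robust variance or another count distribution.

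Two of these analyses enter the fixed sequence in SAP 9.2. Test 18 is "Change in number of hospitalizations for the 12 months post-procedure period" and test 19 is "Change in rhythm disturbance treatments (e.g. electrical or pharmacological cardioversion, AAD therapy, supraventricular ablative therapy) 12 months post-procedure period", each compared with the 12 months before the procedure. Total days hospitalized is an exploratory endpoint in SAP 2.3.5 but is not in the sequence.

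**The concern.** A Poisson distribution gives probability only to 0, 1, 2 and so on. A difference of two counts is negative whenever a subject has fewer events after the procedure than before, and that is the hoped-for result. For rhythm disturbance treatments it is built into the design: subjects must have failed or not tolerated a Class I or III drug (Protocol 4.2), antiarrhythmic drug therapy counts as a treatment (SAP 9.5.5), and subjects are to be weaned at 3 months, with exceptions (Protocol 6.0).

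As written, then, two prespecified tests have no defined likelihood, and someone would have to choose the response variable after data from an open-label trial are in hand. If that choice is the post-period value, a second question follows. Days cluster within stays, so their variance exceeds their mean, and an uncorrected Poisson model gives standard errors that are too small.

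**Working it through.** **Inputs.** The documents give no hospitalization rate, length of stay or dispersion, and no error rate for these analyses, so there is no stated figure to reproduce for this point. The number analysed comes from SAP section 4: 153 subjects at 102:51 with 10% dropout gives 102 × 0.9 ≈ 92 and 51 × 0.9 ≈ 46, or 138 in all. All event rates and stay lengths below are assumptions.

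**Step 1: the literal reading (the change is the response).** With independent Poisson counts before and after,

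P(change < 0) = Σ_j P(post = j) × P(prior > j).

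For means 1 before and 0.5 after: 0.6065 × 0.6321 + 0.3033 × 0.2642 + 0.0758 × 0.0803 + 0.0126 × 0.0190 = 0.383 + 0.080 + 0.006 + 0.000 = 0.47.

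| Prior mean / post mean | Share with negative change (simulated) |
|---|---|
| 0.2 / 0.1 | 0.166 |
| 0.5 / 0.25 | 0.323 |
| 1 / 0.5 | 0.470 |
| 2 / 1 | 0.605 |
| 1 / 1 (no improvement) | 0.345 |

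One negative value is enough to make the likelihood undefined. Even at the lowest share, the chance that none of 138 subjects is negative is 0.834^138, about 10⁻¹¹. In four settings checked trial by trial (0.5/0.5, 1/0.5, 1/1, 2/1), every simulated trial of 138 contained negative values. A Poisson regression fitted to the change stopped with an error.

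**Step 2: the alternative reading (the 6-18 month value is the response, the prior value a covariate).** This can be fitted. If stays are Poisson and each lasts L days, the variance-to-mean ratio of days is φ = E[L²]/E[L]. That equals L for fixed stays and 2m − 1 for geometric stays with mean m. A nominal 5% two-sided Poisson test then has a true level of about 2 × [1 − Φ(1.96/√φ)]. For example, m = 3 gives φ = 5, 1.96/√5 = 0.877, and a level of 38%. The simulated column comes from null trials of 92:46, with 1,000 to 1,500 per scenario. Except at the 1.5-day mean, it covers assumed post-period means of 0.2 to 1.0 stays per subject.

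| Length of stay | φ | Formula | Simulated |
|---|---|---|---|
| exactly 1 day | 1 | 5% | 4-5% |
| mean 1.5, geometric | 2 | 17% | 18% |
| exactly 2 days | 2 | 17% | 16-17% |
| mean 2, geometric | 3 | 26% | 25-30% |
| exactly 3 days | 3 | 26% | 25% |
| mean 3, geometric | 5 | 38% | 36-38% |
| mean 5, geometric | 9 | 51% | 51-53% |

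A mean of 3.3 days gives φ = 5.6 and a level of 41%. A separate simulation at 0.4 stays per subject, 90:45, also gave 41%. Adding heterogeneity between subjects gives 30-31%, 40-42% and 55% at means of 2, 3 and 5 days.

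**Step 3: counts of events under the alternative reading.** Plain Poisson has a type I error of 4-6% if counts are Poisson, and 7%, 8% and 12% with assumed negative binomial heterogeneity of k = 0.5, 1 and 2.

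**Step 4: corrected standard errors.** For days with geometric stays of mean 1.5 to 5, a Pearson scale factor gives 4.5-6.5% and robust variance 5.5-7.6%. For counts with the same heterogeneity, the figures are 4.7-8.0% and 5.2-7.0%.

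**The case against.** The strongest defence is that the post-period count was meant all along. Elsewhere the SAP announces an analysis of a change and then names the follow-up measure as the dependent variable, with baseline as covariate: SF-36, AFSS and walk distance (9.4.2-9.4.4), LVEF (9.5.2) and left atrial size (9.5.3). Including the prior count as a covariate fits that pattern. This stands as a plausible intention. It does not settle the text, because 9.5.4 and 9.5.5 are the sections where no such dependent variable is named. They also exclude withdrawals on the ground that the change is not calculated for them, which treats the change as the analysed quantity.

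It is also fair that these are late exploratory endpoints. Tests 18 and 19 are last in the sequence, are reached only if every earlier evaluated endpoint succeeds, and depend on data being available. That limits the consequence but does not make the tests executable.

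Four stronger inferences are tempting and not supported:

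- **The days analysis has a false-positive rate of about 40%.** That is one assumed length of stay. The documents give none, and the rate is near 5% if all stays last one day.
- **Both faults apply together.** They belong to alternative readings. If the change is the response, the days model cannot be fitted either and has no type I error.
- **Subjects who improve would be dropped.** The SAP prescribes no such exclusion. What happens to negative values depends on the software, and in the check the fit simply failed.
- **The error control of the sequence is damaged by the days analysis.** Days hospitalized is not in the sequence.

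**Conclusion.** The point holds in two conditional parts. On the literal text, tests 18 and 19 and the days analysis cannot be fitted, because the change is negative for roughly 17-60% of subjects under assumed prior/post means of 0.2/0.1 to 2/1. The exact share does not matter, since any negative value is enough.

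On the alternative reading the models can be fitted, but overdispersion is left open. For the counts in tests 18 and 19 the inflation is modest: 4-6% without heterogeneity and 7-12% with the amounts assumed. For days it ranges from about 5% with one-day stays, through 16-18% at a mean of 1.5 days, 25-30% at 2 days and 36-42% at 3 to 3.3 days, to about 50% at 5 days. These figures rest on assumed stay-length distributions and on no variance correction being used.

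Primary and secondary efficacy conclusions are unaffected. What needs correcting is the specification of two last-in-sequence tests and one exploratory endpoint.

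**What to change.** In SAP 9.5.4 and 9.5.5, name the 6-18 month count (or days) as the response, with treatment arm and the prior 12-month value as covariates. The change can still be summarized descriptively. For counts and days, prespecify one way of handling overdispersion: a negative binomial model, or Poisson with robust or Pearson-scaled standard errors. Any of these is adequate, but the choice should be fixed before the 18-month data are analysed.

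A log observed-time offset is optional. Withdrawals before 18 months are excluded and the window is nominally 365 days, so it would usually be nearly constant. The visit windows do allow less: a 6-month visit on day 210 and an 18-month visit on day 520 leave 520 − 210 = 310 observed days.

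The cost is a few sentences of SAP wording, a different distribution or variance option in the program, and slightly wider intervals. No data collection changes.
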